#### **Incomplete Stop Date**

In the case where only the day is missing, the following imputation rules will be applied:

- If the month and year of the incomplete stop date are the same as the month and year of the last IP administration date, then the day of the last IP administration date will be assigned to the missing day;
- If either the year of the partial date is not equal to the year of the last IP administration date or the years of the partial date and the last IP administration date are the same, but the month of partial date is not equal to the month of the last IP administration date, then the last day of the month will be assigned to the missing day.

In the case where both day and month are missing, the following imputation rules will be applied:

- If the year of the incomplete stop date is the same as the year of the last IP administration date, then the day and month of the last IP administration date will be assigned to the missing fields.
- If the year of the incomplete stop date is prior to the year of the last IP administration date or prior to the year of the randomization date, then December 31 will be assigned to the missing fields.
- If the year of the incomplete stop date is prior to the year of the last IP administration date but is the same as the year of the randomization date, then the randomization date will be assigned to the missing date.
- If the year of the incomplete stop date is after the year of the last IP administration date, then January 1 will be assigned to the missing fields.

If the imputed stop date is before the start date, then the imputed stop date will be equal to the start date.

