#### 4.1.2. Exclusion Criteria

Subjects are not eligible to participate in the study if they meet any of the following criteria:

- 1. A primary diagnosis of COPD or asthma as judged by the Investigator. Patients with comorbid COPD and/or asthma can be enrolled if bronchiectasis is their primary diagnosis.
- 2. Subjects receiving supplemental oxygen >12 hours per day.
- 3. Bronchiectasis due to cystic fibrosis.
- 4. Current smokers as defined per CDC: an adult who has smoked 100 cigarettes in his or her lifetime and who currently smokes cigarettes.
- 5. No evidence of bronchiectasis according to the BE-CT scoring system.
- 6. Known or suspected immunodeficiency disorder, including history of invasive opportunistic infections (eg, TB, histoplasmosis, listeriosis, coccidioidomycosis, pneumocystosis, aspergillosis) despite infection resolution, or otherwise recurrent infections of abnormal frequency, or prolonged infections suggesting an immunecompromised status, as judged by the Investigator.
- 7. Known history of HIV infection.
- 8. Established diagnosis of hepatitis B viral infection at the time of Screening, or positive for HBsAg at the time of Screening.
  - Subjects who have gained immunity for hepatitis B virus infection after vaccination (subjects who are HBsAg-negative, HBsAb-positive, and HBcAb-negative are eligible for the study).
  - Subjects with positive HBcAb are eligible for the study only if hepatitis B virus DNA level is undetectable.
- 9. Established diagnosis of HCV infection at the time of Screening. Subjects positive for hepatitis C antibody are eligible for the study only if HCV RNA is negative.
- 10. Currently being treated for NTM lung infection, allergic bronchopulmonary aspergillosis, or TB.
- 11. Active and current symptomatic infection by COVID-19.
- 12. Unable to perform technically acceptable spirometry that meet the ATS/ERS acceptability criteria with at least 3 acceptable flow-volume curves, at least 2 of which meet the ATS/ERS repeatability criteria for FEV1 during Screening.
- 13. Inability to follow the procedures of the study (eg, due to language problems or psychological disorders).
- 14. Receiving medications or therapy that are prohibited as concomitant medications (see Section 5.11.1 for prohibited concomitant medications).
- 15. Started oral or inhaled antibiotics as chronic treatment for NCFBE <3 months prior to the Screening Visit.

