#### **6.2.1.2.1.** Initiating new Chronic Antibiotic Treatment

Initiation of chronic antibiotics will be identified through entries in eCRF "*Prior and concomitant medications*". World Health Organization (WHO) Drug dictionary codes provided in Appendix K will be used to identify start of new chronic antibiotics. The start date of the new chronic antibiotic must be on or after the date of randomization, and at least 7 days from the end of the previous therapy, if applicable. The date entered for "*Start date*" will be used as date of ICE onset.

Note: it is expected that first IP administration is administered at the date of randomization (refer to Section 6.4.2). In circumstances where the date of first IP is not equal to the date of randomization, the date of first IP administration will be used as reference date. Hence, the start date of the new chronic antibiotic must be on or after the date of first IP administration. This rule applies to the below two sub-sections, too.

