#### **Incomplete Start Date**

In the case where only the day is missing, the following imputation rules will be applied:

- If the month and year are the same as the year and month of the first IP administration date, then the first IP administration date will be assigned to the missing day;
- If either the year of the partial date is before the year of the first IP administration date or the years of the partial date and the first IP administration date are the same, but the month of partial date is before the month of the first IP administration date, then the last day of the month will be assigned to the missing day;
- If either the year of the partial date is after the year of the first IP administration date or the years of the partial date and the first IP administration date are the same, but the month of partial date is after the month of the first IP administration date, then the first day of the month will be assigned to the missing day;
- If the stop date is not missing, and the imputed start date is after the stop date, the start date will be imputed by the stop date.

CONFIDENTIAL Page 47 of 139

In the case where both day and month are missing, the following imputation rules will be applied:

- If the year is the same as the year of the first IP administration date, then the day and month of the first IP administration date will be assigned to the missing fields;
- If the year is prior to the year of the first IP administration date, then December 31 will be assigned to the missing fields;
- If the year is after the year of the first IP administration date, then January 1 will be assigned to the missing fields.

In the case where day, month and year are missing, the therapy will be considered as ongoing throughout participant's study participation.

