### Example 02:

- Antibiotics B: start date=15Jun2022, end date=30Sep2022
- Antibiotics B: start date=22Sep2022, end date=ongoing
- In those cases, the start date will be determined as 15Jun2022. The end date will be imputed as defined in Section 6.7.1 for PEs ongoing at EOS or the date of data cut-off for data tabulations during study conduct, e.g., dry-runs.

If exact same therapies are more than 7 days apart (>7), the therapies will be considered as two different therapies.

3. Mark therapies who were stable at baseline:

Any antibiotic therapies started prior to the first administration of IP and who were present at day 1 (baseline), including those ongoing at baseline, and who have a minimum duration of 28 days will be considered as standard of care.

4. Identify standard of care marked therapies who stopped during study conduct. Any standard of care therapies present at baseline but stopped during study conduct will be identified through comparison of the therapy stop date against date of last IP administration. Please refer to Section 6.4.2 for determination of date of last IP administration.

CONFIDENTIAL Page 139 of 139

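### Year-only antibiotic dates: SAP 6.9.2 gives one record two stop dates and can turn an eligible baseline antibiotic into a Day 1 intercurrent event in supplementary analyses

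*SAP*

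**What the plan says.** SAP Section 6.9.2 sets special imputation rules for partial antibiotic dates, to be used when identifying intercurrent events (ICEs).

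**Stop date, day and month missing.** The second bullet begins "If the year of the incomplete stop date is prior to the year of the last IP administration date or prior to the year" and continues "or prior to the year of the randomization date, then December 31 will be assigned to the missing fields". The third bullet repeats the first condition of the second (stop year before the year of last IP) and adds "but is the same as the year of the randomization date, then the randomization date will be assigned to the missing date". A closing line says: "If the imputed stop date is before the start date, then the imputed stop date will be equal to the start date".

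**Start date, day and month missing.** The rule opens "If the year is the same as the year of the first IP administration date, then the day and month of the first IP"; the gaps are thus completed from the first dose. No exception is made for a therapy known to be in use at baseline.

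**What the dates feed.** Section 6.2.1.2.1 requires, for a newly initiated antibiotic, that "the start date of the new chronic antibiotic must be on or after the date of first IP administration" where that date differs from randomization. Appendix M item 3 reserves standard of care for "Any antibiotic therapies started prior to the first administration of IP and who were present at day 1 (baseline") with a duration of at least 28 days. SAP Section 2 permits chronic antibiotics begun at least 3 months before Screening under every estimand. Protocol Section 4.1.2, criterion 15, excludes a participant who "Started oral or inhaled antibiotics as chronic treatment for NCFBE <3 months prior to the Screening Visit".

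**The concern.** The stop-date rules do not define one date per record. Two programmers could each follow the SAP exactly and produce different ICE dates.

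The start-date rule gives one date, but the wrong one for a participant who was already on an eligible chronic antibiotic. It moves the start to Day 1. The therapy then fails the Appendix M test for standard of care and meets the test for an added antibiotic.

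The ICE date ends On-Treatment follow-up (SAP Table 5). An added chronic antibiotic makes a participant a non-responder under the Composite estimand (SAP Section 6.7.2). So a participant on unchanged background therapy could be cut to a single day at risk, or scored as a treatment failure without an exacerbation. The ICE frequencies and time-to-ICE output in Section 8.4 would carry the same error for those participants.

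**Working it through.** No figure in the plan needs reproducing. The check applies the year-only rules literally to every randomization date in a 365-day year.

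Inputs and assumptions: first IP on the randomization date; last IP on Day 364 (randomization + 363 days); screening 1 to 42 days before Day 1 (Protocol Section 3.3 allows up to 6 weeks); 3 months taken as 91 days; time at risk = ICE onset − first IP + 1, before subtracting exacerbation days (SAP Table 5); an added antibiotic counts as an ICE only if taken for more than 28 days (SAP Section 2).

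**1. Stop date: how often both bullets apply.** Both apply when the stop year equals the randomization year and last IP falls in the next calendar year.
- Randomization on 1 January puts last IP on 30 December, and 2 January puts it on 31 December. Every later date puts it in the next year.
- Overlap: 365 − 2 = 363 dates, and 363/365 = 99.5%.

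**2. Stop date: how far apart the two dates are.** For a baseline therapy the gap is December 31 minus the randomization date. It runs from 0 days (31 December) to 362 days (3 January), with mean (0 + 362)/2 = 181 days.
- Baseline therapy, randomized 01 Mar 2022, last IP 27 Feb 2023, stop recorded as 2022 only. The stop is 31 Dec 2022 (Day 306) or 01 Mar 2022 (Day 1). Taking the stop date as ICE onset, as Section 6.2.1.2.3 does for a changed antibiotic, On-Treatment follow-up is 306 days or 1 day.
- Therapy begun 10 Jun 2022 in the same participant. December 31 gives 205 days of use, which exceeds 28 and is an ICE. The randomization date precedes the start, so the stop is reset to 10 Jun: 1 day of use and no ICE. The two stop dates are 204 days apart, against 305 for the baseline therapy.

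**3. Start date: effect on an eligible baseline therapy.** True start 15 Feb 2022, recorded as 2022 only; screening 02 Aug 2022; first IP 01 Sep 2022.
- Start to screening is 168 days, so the 3-month requirement is met.
- The imputed start is 01 Sep 2022, which is Day 1. It is not before first IP, so it is not standard of care. It is on or after first IP, so it is an added antibiotic if use continues beyond 28 days.
- On-Treatment time at risk: 1 day instead of up to 364. Composite: non-responder, which changes the outcome only if the participant would otherwise have been a responder.

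**4. Start date: when the calendar allows this.** A same-year eligible start needs first IP at least 91 days plus the screening length after 1 January.
- Screening 1 day: 365 − (91 + 1) = 273 dates, or 75%.
- Screening 42 days: 365 − (91 + 42) = 232 dates, or 64%.

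**5. Scale.** SAP Section 2 puts chronic antibiotic use at about 20% of participants: 0.20 × 1,620 = 324 adults. The share with year-only dates is not given. If it were 1%, 5% or 10% (assumed), about 3, 16 or 32 participants would have such a date, and fewer would meet the same-year condition.

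**6. Reach.** SAP Tables 1 and 2 handle changes to standard of care by treatment policy in every On-Study and On-IP estimand, so none of the 12 hypotheses in SAP Table 3 uses these dates. What remains is the On-Treatment analysis of the primary endpoint, the Composite responder analysis, the Section 8.4 summaries, and the jump-to-reference analysis in Section 8.2.4 if it is run. Under the Composite estimand, stopping standard of care is treatment policy, so the stop-date conflict reaches it only through the 28-day test. The start-date rule reaches it directly.

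**The case against.** The strongest case on the other side has four parts.

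- **The third stop bullet reads as an exception to the second.** It restates the condition and narrows it. That is plausible, but the text does not say so. Even on that reading, a baseline therapy stopped at an unknown time in the randomization year is dated to Day 1.
- **Safeguards exist.** SAP Section 6.9 imputes only after efforts to obtain the data fail. SAP Section 6.2 has a blinded review of participants meeting ICE criteria, with agreed actions signed before lock and unblinding. A background antibiotic flagged on Day 1 might well be caught there. Neither safeguard states a corrected date rule.
- **The figures describe opportunity, not frequency.** This stands. The 99.5% assumes dosing to Day 364; if last IP falls in the randomization year, a same-year stop comes under the first bullet alone. The 181-day mean applies only to baseline therapies. The 64% to 75% is the share of calendar dates on which the start problem is possible; multiplied by the 20% on chronic antibiotics it does not give a prevalence.
- **An imputation convention cannot contradict an eligibility rule.** This also stands. Criterion 15 covers oral or inhaled chronic treatment for bronchiectasis, while Appendix K captures systemic antibacterials with few route exclusions and no limit by indication. The point is only that the imputed date is impossible for a therapy that met criterion 15.

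A reader might infer that the antibiotic ICEs in general are misdated or false, or that the primary result is at risk. The documents support neither. Both defects need day and month missing and a matching year. A start date missing only its day cannot affect a baseline antibiotic begun at least 3 months before Screening. A year-only start in an earlier year goes to December 31 of that year and stays before Day 1.

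**Conclusion.** Both defects stand as written, for records missing both day and month. The stop-date bullets overlap without precedence, on 363 of 365 randomization dates for a participant dosed to Day 364. The competing dates are up to 362 days apart (mean 181, with randomization dates spread evenly over the year) for a baseline therapy, and closer together for one begun after randomization. The start-date rule can turn an eligible baseline antibiotic into a Day 1 ICE, leaving 1 day of On-Treatment follow-up and a Composite non-response.

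The number of such records is unknown, so no effect on any estimate has been shown. Confirmatory inference is unaffected. The correction is still worth making: SAP Section 2 gives the On-Treatment estimand a role in describing benefit-risk and cost-effectiveness, and the rules should give one defensible date per record before unblinding.

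**What to change.** In SAP Section 6.9.2:

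1. Restrict the December 31 stop bullet to stop years other than the randomization year. State one date for the remaining same-year case, chosen before unblinding, so that every record has a single imputed stop.
2. For a year-only start in the year of first IP, impute a date before first IP, so that the therapy counts as baseline standard of care, when available data show use before Day 1. Examples are medication reported at Screening or Baseline (Protocol Table 5 collects it at both) or medical history. Otherwise keep the first-IP date.

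The cost is a short SAP edit, minor programming, and blinded review of the affected records. The documents do not confirm that the medication form stores the visit at which a therapy was first reported, so the second rule should rest on whatever evidence is available and not on that field alone.

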#### 6.9.3. Missing Start and Stop Dates for Adverse Events

The rules to categorize AEs to 'TEAE' or 'non-TEAE' are described in Section 9.2. There is no need to impute missing or partially missing start or stop dates.

CONFIDENTIAL Page 48 of 139

#### 6.9.4. Missing Dates for Time since Diagnosis

The following rules will be applied for partial dates of bronchiectasis diagnosis:

- if only the day is missing, the first day of the month will be assumed;
- if the day and the month are missing, January 1st will be assumed.

#### 7. STUDY POPULATION SUMMARIES

Data will be displayed separately by treatment groups and total (see Section 6.4.2) unless otherwise stated.

### 7.1. Participant Disposition

The participant disposition will be based on the Screened Analysis Set (see Section 5.1).

For participants screened, the number of participants who are screened, the number and percent of participants who continue into the study, and the number of participants who failed screening, the reasons for screen failure, and relationship of screen failure to COVID-19 will be summarized. In addition, the participant disposition will include the number and percentage of participants who are:

- randomized,
- excluded from analysis due to war in Ukraine,
- excluded from analysis due to serious GCP noncompliance (site USA065),
- did not receive IP,
- completed/discontinued from the study or IP and the reason for discontinuation (including relation to COVID-19),
- ongoing study or IP at primary database lock.

Number of participants included in each of the analysis sets will be summarized as counts and percentages, too.

#### 7.2. Protocol Deviations

Deviations from the study protocol will be monitored throughout the conduct of the study.

Major protocol deviations that may affect the primary efficacy and/or safety assessments (as applicable), the safety or mental integrity of a participant, or the scientific value of the study will be summarized descriptively. Tabulations will be based on the ITT Analysis Set (see Section 5.2).

CONFIDENTIAL Page 49 of 139

### 7.3. Demographic and Baseline Characteristics

Demographic and baseline characteristic variables will be summarized for all Analysis Sets as defined in Section 5. A summary by region will be provided, too. The summary will include:

Insmed Incorporated

- country,
- age,
- age group (12 to <18 years, 18 to <65 years, >= 65 years),
- age group >=18 years,
- age group (<75 years, >=75 years),
- sex,
- ethnicity,
- race,
- Baseline height,
- Baseline BMI,
- Baseline FEV1, pre- and post-bronchodilator (in L and % Predicted),
- Baseline FEV1 (% Predicted) < 50%,
- History of Chronic Obstructive Pulmonary Disease, identified through MedDRA coded terms (see Appendix K),
- History of Asthma, identified through MedDRA coded terms (see Appendix K),
- Hospitalized in prior 24 months for PE,
- CT Scan confirmation of Bronchiectasis,
- Use of Inhaled Steroids, identified through ATC coded terms (see Appendix K),
- Chronic use of Antibiotics,
- Bronchiectasis Severity Index (BSI) (see Appendix L),
- BSI categories (<=4, 5-8, >=9),
- Smoking status, including pack-years smoked (refer to Section 6.4.6 for calculation of pack-years smoked),
- Baseline eosinophil count (>=300/mm3, <300/mm3),
- Baseline QoL-B Respiratory Symptoms Domain Score (adults),
- Baseline BE-CT Score
- the stratification variables region (North America, Europe, Japan, and Rest of World), sputum sample (positive or negative for *Pseudomonas aeruginosa*) and the number of PEs in the previous 12 months (<3, >=3). Stratification variables will be presented as used for randomization.
- Geographic Region (South America, Eastern Europe, Western Countries, Asian Countries)

The distribution of participants randomized across region, country, and site will be presented for the ITT analysis set.

In addition, a listing will be produced for mismatches between randomized and actual strata.

CONFIDENTIAL Page 50 of 139

#### 7.3.1. Medical History and Indication History of NCFBE

All medical history records will be coded using Medical Dictionary for Regulatory Activities (MedDRA). The incidence of medical history abnormalities will be summarized for the ITT and Safety Analysis Set using counts and percentages by System Organ Class (SOC) and Preferred Term (PT). Participants are counted only once in each SOC and only once in each PT.

Indication history will summarize the time since bronchiectasis diagnosis, etiology, PEs reported in the past 12 months before screening, and whether antibiotic prescription was documented.

The time since diagnosis will be calculated as below. For handling partial dates, refer to Section 6.9.4.

time since diagnosis (days) = date of randomization – date of bronchiectasis diagnosis – +1.

## 7.4. COVID-19 Impact

Potential COVID-19 impact is captured in the eCRF and will be summarized by participant. Participant disposition summary and listing will include (see Section 7.1):

- Screen failure related to COVID-19,
- Treatment discontinuation related to COVID-19,
- Early termination of study related to COVID-19.

AE overview table and listings will include (see Section 9.2):

- COVID-19 AEs.
- In addition, correlation between COVID-19 AEs within +/-30 days of an exacerbation event that meet the protocol definition of PE diagnosis based on independent adjudication process start and end date will be investigated (see Section 9.2).
- COVID-19 AEs by region and time period:
  - O Start of study to 30-Jun-2021
  - o 01-Jul-2021 to 15-Dec-2021
  - o since 16-Dec-2021

Summary table and listing of missed IP / IP discontinuation will include (see Section 9.1):

- Missed IP due to COVID-19.
- IP discontinuation due to COVID-19.

Summary and listing of protocol deviations will include (see Section 7.2):

• Protocol deviations due to COVID-19.

CONFIDENTIAL Page 51 of 139

